8.3 ADVERSE EVENTS

All serious adverse events will be presented in a table and in which study arm they occurred . AE's will be coded by SOC and presented in a table with number and study arm.

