4 STUDY POPULATION

4.1 NUMBER OF PARTICIPANTS

Number: 135 participants.

Recruitment period: 22 months

Dropout rate: it is anticipated that the dropout rates will vary depending on which group they have been randomised to. Assuming 10%, 15%, and 20% drop-out rates in the TC, EC-nicotine & EC-nicotine free groups respectively, we will require 135 participants to provide a final evaluable sample of 112 participants.

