5.5 RANDOMISATION

5.5.1 Randomisation

Randomisation will be carried out in a 1:1 fashion for the 2 randomised arms via a centrally controlled web-based GCP compliant randomisation system, TRUsT, run by Tayside Clinical Trials Unit (TCTU). To ensure balanced assignment across critical variables, a minimisation algorithm will be employed, using baseline age (≤ 40 years; > 40 years), sex (male; female) and smoking pack years (≤ 20 pack years; > 20 pack years). Randomisation will be performed by the PI, researcher or other local delegated individual.

Recruitment will stop when the required number is reached in each arm (maximum 45 per arm)

The TC arm will not be randomised.

To facilitate recruitment and minimise dropouts we propose to recruit the TC smoking arm as a separate non randomised group. Potential participants will be identified and approached in exactly the same ways as for the 2 EC arms. All participants will be asked if they wish to continue to smoke TC or to be randomised to one of the EC arms. This will enable us to recruit volunteers who would find it too difficult to stop their TC for 4 weeks. It will also avoid disappointment for those volunteers who are ready to stop smoking and do not wish to continue with their TC, which has the potential to lead to further dropouts. This is an unblinded study with the exception of the measurement of endothelial function and vascular stiffness which will be performed by a single blinded operator.

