5.5.3 Withdrawal procedures

When participants withdraw from active treatment the study team will ask them if they are willing to remain in the study and complete the study assessments.

If participants withdraw from the study and do not wish to return for study visits, contact with them will be maintained by the PI, trial manager, researcher or research assistant to ensure resolution of adverse event(s). If withdrawal is due to an AE it will be logged as such on the Adverse Event Log.

Participants are free to withdraw from the study at any time. The reasons, if known, will be recorded in the medical casenotes and CRF. Although a participant is not obliged to give reason(s) for withdrawing prematurely, if the participant appears lost to follow up, the CI will make a **reasonable** effort to ascertain the reason(s), while fully respecting the individual’s rights, and will demonstrate that everything possible was done in an attempt to find any participant lost to follow-up. Those lost to follow-up or withdrawn will be identified and a descriptive analysis of them provided, including the reasons for their loss and its relationship to treatment and outcome.

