9 SERIOUS ADVERSE EVENTS

9.1 RECORDING AND REPORTING SAEs

Adverse events will not be recorded in this non-CTIMP study unless they are deemed as serious (SAE). All SAE will be recorded in a SAE Log.

A serious adverse event (SAE) is defined as an untoward occurrence that:

- results in death;
- is life-threatening;
- requires hospitalisation or prolongation of existing hospitalisation;
- results in persistent or significant disability or incapacity;
- consists of a congenital anomaly or birth defect;
- or is otherwise considered medically significant by the investigator

Note: Hospitalisations for treatment planned prior to randomisation and hospitalisation for elective treatment of a pre-existing condition will not be considered as an SAE. However any serious adverse events occurring during such hospitalisation will be recorded.

An SAE occurring to a research participant will be reported to the main REC and Sponsor where in the opinion of the Chief Investigator (CI) the event was:

Related – that is, it resulted from administration of any of the research procedures, **and**

Unexpected – that is, the type of event is not listed in the protocol as an expected occurrence.

Other SAE will not be reported.

SAEs will be reported as per HRA guidelines to the REC and Sponsor:

	Who	When	How	To whom
SAE	Chief Investigator (CI)	Within 15 days of the CI becoming aware of the event	SAE report form for non-CTIMPs	Main REC for the trial. Sponsor
Urgent safety measures	Chief Investigator (CI) or sponsor Or exceptionally by local principal investigator (PI)	(i) Immediately (ii) Within 3 days	(i) By telephone (ii) Notice in writing setting out the reasons for urgent safety measures and the plan for further action	Main REC, trial REC co-ordinator will acknowledge within 30 days Sponsor

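### SAP 8.3 plans an adverse-event table by SOC and arm, but the protocol collects only serious events and those behind withdrawals, so the table could reflect drop-out rather than safety

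*SAP*

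**What the plan says.** SAP 8.3 has two sentences, and they describe two outputs. The first covers serious events: "All serious adverse events will be presented in a table and in which study arm they occurred". The second covers adverse events without that qualifier: "AE's will be coded by SOC and presented in a table with number and study arm".

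Protocol 9.1 sets the collection rule: "Adverse events will not be recorded in this non-CTIMP study unless they are deemed as serious (SAE"). It names one log: "All SAE will be recorded in a SAE Log". The Study Matrix in Protocol 3.3 agrees with it. Its only safety row is for serious adverse events, marked at week 4.

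Protocol 5.5.3 contains an exception that 9.1 does not mention: "If withdrawal is due to an AE it will be logged as such on the Adverse Event Log". The same section promises a descriptive analysis of participants lost or withdrawn, with their reasons and how these relate to treatment and outcome. SAP 5.3 says reasons for drop-out will be ascertained and tabulated.

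Drop-out is expected to differ by group. Protocol 4.1 states: "Assuming 10%, 15%, and 20% drop-out rates in the TC, EC-nicotine & EC-nicotine free groups respectively".

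**The concern.** Taken together, these sections give the SOC table no source of non-serious events except the withdrawal log. A participant with a non-serious event who stays in the study contributes nothing. One who leaves because of the same event contributes a count. Whether an event is recorded then depends on withdrawal, and the plan itself expects withdrawal to be more frequent in the EC arms.

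A table of adverse events by arm will be read as a safety comparison of EC with TC, and how safe EC are is a question that the protocol's background asks outright. Protocol 5.5.1 makes such a reading harder still, because the TC arm is self-selected and participants know what they are using. The stake is a misleading or empty safety table. FMD is not involved.

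**Working it through.** **1. The three readings of the text.**

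- Protocol 9.1 governs alone: only serious events exist in the data. The SOC table repeats the serious-event table with coding added, and drop-out has no effect on it.
- The Protocol 5.5.3 log feeds SAP 8.3: non-serious events are counted only among participants who withdrew.
- Site staff settle the conflict case by case: ascertainment is undefined.

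None of these yields a table of all adverse events by arm.

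**2. The plan's own numbers.** Protocol 8.1 needs 36 completers per group. Inflating for drop-out, n = 36/(1 − d):

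- TC: 36/0.90 = 40
- EC-nicotine: 36/0.85 = 42.4, rounded up to 43
- EC-nicotine free: 36/0.80 = 45

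Using the largest for every arm gives 3 × 45 = 135, the stated total. It also matches Protocol 5.5.1: "Recruitment will stop when the required number is reached in each arm (maximum 45 per arm"). Expected completers are 40.5 + 38.25 + 36 = 114.75, close to the stated figure: "we will require 135 participants to provide a final evaluable sample of 112 participants".

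**3. Expected drop-outs, all causes (45 × d).**

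- TC: 45 × 0.10 = 4.5
- EC-nicotine: 45 × 0.15 = 6.75
- EC-nicotine free: 45 × 0.20 = 9
- Total: 20.25

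Share in the two EC arms: 15.75/20.25 = 78%. With equal drop-out it would already be 90/135 = 67%, because two of the three arms are EC. Differential drop-out adds about 11 percentage points.

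If recruitment instead stops at 36 completers per group, drop-outs are 40 − 36 = 4, 42.35 − 36 = 6.35 and 45 − 36 = 9. The EC share is then 15.35/19.35 = 79%, so the pattern does not depend on which stopping rule applies.

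**4. Expected logged events.** Let f be the share of drop-outs caused by an adverse event. The documents do not give f, so the values below are assumptions, equal across arms. Expected count = 45 × d × f, with one logged event per such withdrawal and drop-out standing in for withdrawal. The last two columns treat each arm's count as an independent binomial with n = 45 and probability d × f.

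| Assumed f | TC | EC-nicotine | EC-nicotine free | P(EC-nicotine count > TC) | P(EC-nicotine free count > TC) |
|---|---|---|---|---|---|
| 10% | 0.45 | 0.68 | 0.90 | 36% | 45% |
| 25% | 1.1 | 1.7 | 2.25 | 51% | 63% |
| 50% | 2.25 | 3.4 | 4.5 | 61% | 76% |

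**5. When the expected excess disappears.** Counts are equal on average if the TC share f is 0.20/0.10 = 2 times the EC-nicotine free share, or 0.15/0.10 = 1.5 times the EC-nicotine share. At f = 0 every count is zero.

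**The case against.** The strongest reply is that this is a wording slip with little consequence. SAP 8.3 names no data source, and neither document says that the Adverse Event Log feeds it. Read with Protocol 9.1, the second sentence may mean only that serious events will be coded by SOC. The 10/15/20% rates are for all causes, and the reasons discussed in Protocol 5.5.1 are difficulty giving up TC and disappointment for those ready to stop, not adverse events. Some participants will be lost without a known reason. SAP 8.3 promises counts, with no rate or test, and safety is not among the objectives or outcomes. Protocol 5.5.3 and SAP 5.3 already promise a description of withdrawals, which would help a reader interpret an imbalance.

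Most of this stands, and it limits the size of the point. A reader might infer that the table will show a safety difference against the EC arms. The documents do not support that. It would need the withdrawal log to feed the table, a material share of drop-outs to be caused by adverse events, and a similar share in each arm. None of these is stated. Nor should the 78% be read without the 67% that equal drop-out would give.

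The reply does not remove the contradiction. SAP 8.3 separates serious events from adverse events, Protocol 9.1 and 5.5.3 disagree on what is recorded, and the drop-out descriptions are separate outputs that neither label nor restrict the SOC table.

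**Conclusion.** The inconsistency between SAP 8.3, Protocol 9.1 and Protocol 5.5.3 is established from the text. As planned, the SOC table either duplicates the serious events or counts non-serious events only among participants who withdrew, and in the second case it could show a by-arm difference that reflects drop-out rather than safety.

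The likely size is modest. For assumed adverse-event shares of 10% to 50%, equal across arms, the expected excess of EC-nicotine free over TC runs from 0.45 to 2.25 events. At 10%, an excess is less likely than not. The direction rests on assumptions that the documents do not supply. Neither the primary FMD analysis nor its sample size is affected. The point is worth correcting because the correction costs little and the table cannot be supported by the data collected.

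**What to change.** Reconcile SAP 8.3 with Protocol 9.1 and 5.5.3. The preferred route has two parts:

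- Limit SAP 8.3 to serious adverse events, coded by SOC and shown by arm.
- Report withdrawals due to an adverse event by arm within the drop-out table already promised in Protocol 5.5.3 and SAP 5.3, with a footnote that non-serious events were ascertained only through withdrawal and that the counts are not comparative adverse-event frequencies.

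This costs a few lines of SAP wording and no new data. A cross-reference from Protocol 9.1 to the log in 5.5.3 would close the remaining gap and can go in with the next protocol amendment.

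If the sponsor prefers to keep a table of all adverse events, Protocol 9.1 must be amended so that events are collected in the same way in all three arms, at withdrawal as well as at week 4. A week-4 question alone would miss participants who do not return, so ascertainment would still depend on drop-out. This route needs an amendment with Sponsor, REC and NHS R&D approval under Protocol 12.1, and a week-4 question introduced part-way would not reach participants who have already finished.

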9 REPORTING CONVENTIONS

P-values ≥0.001 will be reported to 3 decimal places; p-values less than 0.001 will be reported as "<0.001". The mean, standard deviation, and any other statistics other than quantiles, will be reported to one decimal place greater than the original data. Quantiles, such as median, or minimum and maximum will use the same number of decimal places as the original data. Estimated parameters, not on the same scale as raw observations (e.g. regression coefficients) will be reported to 3 significant figures.

References:

- 1. Khan, F., et al., Lowering of oxidative stress improves endothelial function in healthy subjects with habitually low intake of fruit and vegetables: A randomized controlled trial of antioxidant- and polyphenol-rich blackcurrant juice. Free Radic Biol Med, 2014. 72: p. 232-7.
- 2. Dmitrienko A, C.-S.C., *Pharmaceutical Statistics Using SAS: A Practical Guide (SAS Press) SAS Institute*2007.
